**Table 3: Dose Adjustments for Hematological Toxicity**

Situation	Doxil Dose
First episode of febrile neutropenia (grade 3 or 4)	75%
Second episode of febrile neutropenia (grade 3 or 4)	Discontinue
Grade 4 thrombocytopenia or bleeding associated with thrombocytopenia	75%

In addition to the above dose adjustments, subjects experiencing febrile neutropenia secondary to Doxil may receive G-CSF therapy in association with subsequent chemotherapy doses.

**Table 4: Dose Adjustments for Other Toxicities**

NCI CTC Grade	Doxil Dose
0 - 2	100%
3 (except alopecia)	75%
4	Hold until resolution of toxicity

## 8. Study Statistics

8.1. **Statistical Methods:** This study is a prospective single arm Phase II trial to assess association of BRCA1 protein expression with overall response rate in patients with metastatic breast cancer on pegylated liposomal doxorubicin in patients with metastatic breast cancer. We plan to consent 50 to 60 patients with the goal of enrolling a total of 50 patients, with adequate primary tumor tissue for BRCA1 protein expression, into this study. It is estimated that 30% of patients will have low BRCA1 protein expression and therefore anticipate approximately a 35 to 15 patient split for normal BRCA1 to low BRCA1 expression status.

Recruitment and tissue analysis: Patients will be consented and after enrollment of the first 12 patients, a batch analysis of their tumors will be performed to analyze tumor BRCA1 protein expression. This will allow us to assign the patients to their respective cohorts (Normal BRCA1 protein expression and Low BRCA1 protein expression). This will be done until we have 12 patients in the normal BRCA1 protein arm. After that, an interim analysis will be performed for the normal BRCA1 arm and stopping rule will be applied as mentioned in the study design

8.2. **Analytic plan for primary objective:**

**Definition of primary endpoint:** Response rate is defined as the percentage of evaluable patients who achieve complete response (CR) or partial response (PR) as measured by RECIST on imaging as the best overall response.

**Low BRCA1 protein expression:** The number and percentage of patients falling into response category will be tabulated. The estimate of the response rate will be presented with 2-sided 95% exact binomial confidence intervals. We anticipate this data to be hypothesis generating and will form the basis for a future prospective clinical trial enrolling larger number patients to evaluate if low BRCA1 expression, as determined by IHC, is predictive of response to treatment with DNA damaging agents.

**Normal BRCA1 protein expression:** The estimate of the response rate will be presented with 2-sided 95% exact binomial confidence intervals. If 5 or fewer patients with response are observed among the 35 patients, then there will be no further investigation of the treatment. If 6 responses are observed out of 35 patients, there is 80% confidence that the true response rate >11.2%.

Interim analysis:

**Low BRCA1 protein expression:** No interim analysis will be conducted

**Normal BRCA1 protein expression:** An interim analysis for futility will be conducted for this arm. The response rate will be used as the endpoint for the interim analysis. The interim analysis will be performed when the first 12 treated patients are accrued to normal BRCA1 protein expression arm. Based on Simon's 2-stage design, if less than 2 responders are observed out of these initial 12 evaluable patients, patient enrollment will be discontinued into this arm. Otherwise patient enrollment will continue until a total of 35 patients evaluable for response are enrolled. If only 1 response is observed out of 12 patients, there is 80% confidence that the true response rate <22.1%.

If the normal BRCA1 protein expression arm is closed to accrual, we will continue to consent patients who are being treated with pegylated liposomal doxorubicin. As the expression of BRCA1 protein is anticipated to be low in only 30% of patients, we will continue to consent patients and analyze their tumors and only those with low BRCA1 protein expression will be enrolled into the arm. We anticipate consenting total of 50-60 patients to enroll 15 patients into the low BRCA1 protein expression arm.

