**Exclusion Criteria** The following will exclude patients from study participation Myocardial infarction within 6 months of registration Brain metastases unless documented to be controlled post completion of local therapy (surgery and/or radiation therapy) for at least four weeks prior to registration Pregnant or breast feeding women. Women with child bearing potential must use effective measures to prevent pregnancy while receiving pegylated liposomal doxorubicin Have a concurrent active non-breast malignancy except for non-melanoma skin cancer Have a concurrent active non-breast malignancy except for non-melanoma skin cancer Her2 positive tumors as defined by FDA guidelines (3+ immunohistochemical staining, defined as uniform, intense membrane staining of more than 10% of invasive tumor cells, and for cases with 2+ staining showing gene amplification by FISH, expressed as a ratio of more than 2 when comparing HER-2 gene and chromosome 17 fluorescent signals)

**Intervention:** Patients with metastatic breast cancer treated at the University of Arizona Cancer Center and University of New Mexico Cancer center will be enrolled in this trial. Patients whose treatment for their tumor includes liposomal doxorubicin are eligible to take part in this study. Their primary tumors will be obtained for evaluation of BRCA1 protein expression. When primary tumor is not available, paraffin embedded metastatic tumor will be tested for BRCA1 protein expression. Patients will receive pegylated liposomal doxorubicin intravenously at  $30\text{mg}/\text{m}^2$  every 21 days.

**Duration of Intervention:** Patients will get a baseline PET/CT or CT chest/abdomen/pelvis scan prior to receiving pegylated liposomal doxorubicin. We will repeat the same imaging scan at 9-12 weeks to evaluate response by RECIST 1.1. Pegylated liposomal doxorubicin will be stopped if there is evidence of disease progression. Also, it will be discontinued if there is development of persistent  $\geq$  grade 3 fatigue or non-reversible  $\geq$  grade 4 hematological or renal or liver abnormalities or if the patient chooses.

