### Sample size determination

**Low BRCA1 protein expression:** Since it is expected only 30% of patients will have low BRCA1 protein expression, we will accrue 15 patients to this arm and estimate the response rate among these patients. With a sample size of 15 we will be able to estimate the response rate of 50% in patients with low BRCA1 protein expression with a 95% confidence interval width of  $\pm 25\%$ .

**Normal BRCA1 protein expression:** A Simon two-stage design will be used in which a 10% response rate is considered not promising, a 30% response rate is considered promising, and the probabilities of a type I error (falsely accepting a non-promising therapy) and type II error

(falsely rejecting a promising therapy) are set at 0.10 and 0.10, respectively. In this scenario, the maximum trial size would be 35 patients. In the first stage of this design, 12 patients with intact BRCA1 expression will be accrued. If at least two responses are observed among these 12 patients, then an additional 23 patients will be accrued to the second stage. If 0 or 1 response is observed among the initial 12 patients, then accrual to this cohort will be terminated and declared negative. At the end of the study if 6 or more patients in this cohort respond then pegylated liposomal doxorubicin will be considered worthy of further study in this cohort. This design yields at least 90% probability of a positive result if the true response rate is at least 30% and a 90% probability of a negative result if the true response rate is 10%.

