#### **Interim Analysis**

**Low BRCA1 protein expression:** No interim analysis will be conducted

**Normal BRCA1 protein expression:** An interim analysis for futility will be conducted in this group. The response rate will be used as the endpoint for the interim analysis for this group. The interim analysis will be performed when the first 12 treated patients are accrued. Based on Simon's 2-stage design, if less than 2 responders are observed out of these initial 12 evaluable patients in normal BRCA1 protein expression, patient enrollment will be discontinued into this arm. Otherwise patient enrollment will continue until a total of 35 patients evaluable for response are enrolled. If only 1 response is observed out of 12 patients, there is 80% confidence that the true response rate <22.1%.

**Feasibility Issues:** Patients with metastatic breast cancer (exclude Her-2/neu patients) whose primary tumor tissue is available for assessing defective DNA repair will be identified by the medical oncologists at the University of Arizona Cancer Center and the University of New Mexico to be included and treated with pegylated liposomal doxorubicin in the salvage setting. During the past year we have treated more than 25 patients with metastatic breast cancer with liposomal doxorubicin. We anticipate to complete accrual of 50 patients in 2 years. If we do not

accrue as expected after year 1, we plan to expand enrollment to other institutions we are currently collaborating (University of Washington and University of New Mexico).

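### If the normal-BRCA1 cohort stops at 0 or 1 of 12, does the plan leave open how to treat the normal patients already enrolled beyond those 12?

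*Combined protocol and SAP*

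**What the plan says.** Section 8.1 describes recruitment and typing: "after enrollment of the first 12 patients, a batch analysis of their tumors will be performed to analyze tumor BRCA1 protein expression", and "This will be done until we have 12 patients in the normal BRCA1 protein arm". The size of later batches is not given. Section 8.2 times the look: "The interim analysis will be performed when the first 12 treated patients are accrued to normal BRCA1 protein expression arm". The stopping rule follows: "if less than 2 responders are observed out of these initial 12 evaluable patients, patient enrollment will be discontinued into this arm".

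The consequence of stopping appears in the synopsis under Sample size determination: "If 0 or 1 response is observed among the initial 12 patients, then accrual to this cohort will be terminated and declared negative". Section 9 repeats it in its paragraph on study closure, and section 8.1 refers back to the study design for the stopping rule. The end-of-study rule in section 8.2 concerns a full cohort: "If 5 or fewer patients with response are observed among the 35 patients, then there will be no further investigation of the treatment".

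On timing, the synopsis (Duration of Intervention) says "We will repeat the same imaging scan at 9-12 weeks to evaluate response by RECIST 1.1", and Feasibility Issues says "We anticipate to complete accrual of 50 patients in 2 years". Section 8.1 expects 30% of patients to be low.

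On estimation, section 8.2 defines response rate over evaluable patients with an exact 95% interval, and section 8.3 plans Kaplan-Meier PFS for the patients in each BRCA1 group. Appendix 2 (Reporting of results) places all eligible patients in the main response analysis and counts those who cannot be assessed as failures.

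**The concern.** A futility look that needs 12 scan results cannot be read on the day the twelfth normal patient enrols. If accrual continues meanwhile, the cohort ends with more than 12 patients and fewer than 35, and section 8 gives rules only for those two sizes. Three questions then seem unanswered: which 12 patients decide, whether a response in a later patient can undo the stop, and whether later patients enter the response rate and PFS.

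The normal cohort is the trial's only internal reference for the question of whether low expression favours response. A cohort closed for few responses has a rate biased downward, which flatters the low-BRCA1 group. If the stop could be undone by later responses, type I error would exceed the stated 0.10.

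**Working it through.** **1. The plan's own design.** Inputs from Sample size determination: null rate 0.10, target rate 0.30, stop at 1 or fewer of 12, positive at 6 or more of 35.

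P(positive) = Σ over x = 2 to 12 of b(x; 12, p) × P(at least 6 − x responses among 23).

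This gives 0.098 at p = 0.10 and 0.901 at p = 0.30. A search confirms 1/12, 5/35 as Simon's optimal design, so the stated figures reproduce.

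**2. Size of the overrun.** 50 patients in 2 years is 25 a year, and 70% normal makes 17.5 normals a year. Assume steady accrual and no pause.

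- 9-week wait: 17.5 × 9/52.18 = 3.0, total 15.0.
- 12-week wait: 17.5 × 12/52.18 = 4.0, total 16.0.
- Two typing batches of 12 (later batch size assumed): 24 × 0.7 = 16.8 normals.

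So 15-17 is a fair expectation if accrual is not held.

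**3. The verdict.** The synopsis and section 9 both attach a negative declaration to the result in the initial 12. Under that rule the overrun has no role, and the error rates in step 1 are unchanged. A rule that let the cohort reopen on 2 or more responses among 15, 16 or 17 would have type I error 0.115, 0.118 or 0.122, but the plan contains no such rule. Nor could the overrun reach the final bar of 6. After a stop, the most possible is 1 + 3 = 4 responses among 15, or 1 + 4 = 5 among 16. With 17 patients it needs 1 in the first 12 and all 5 later patients responding. The joint probability of stopping and reaching 6 is then 0.000004 at a true rate of 10% and 0.00017 at 30%.

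**4. The estimate.** Let p be the true normal rate. The three scenarios are the null (10%), the cited overall rate (25%), and a derived value, (0.25 − 0.3 × 0.5)/0.7 = 14.3%, which assumes 25% overall and 50% in the low group.

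P(stop) = (1−p)^12 + 12p(1−p)^11.

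E[X | stop] = 12p(1−p)^11 / P(stop).

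Shortfall on n patients = p − (E[X | stop] + (n−12)p)/n, which equals 12/n times the shortfall on the 12 alone.

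| True rate | P(stop) | E[X given stop] | Shortfall, n = 12 | Shortfall, n = 17 | P(stop) × difference |
|---|---|---|---|---|---|
| 10% | 0.659 | 0.571 | 5.2 points | 3.7 points | 1.0 point |
| 14.3% | 0.472 | 0.667 | 8.7 points | 6.2 points | 1.2 points |
| 25% | 0.158 | 0.800 | 18.3 points | 12.9 points | 0.9 point |

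Including the later patients leaves 12/17 = 71% of the conditional shortfall in place.

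**5. Precision of the contrast.** With 15 low patients at 50%, the 95% half-width for low minus normal is 1.96 × √(0.25/15 + p(1−p)/n). Going from n = 12 to 17, it moves from 30.5 to 29.0 points at 10%, from 32.1 to 30.3 at 14.3%, and from 35.2 to 32.6 at 25%. The 15 low patients dominate it.

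**The case for a change.** The strongest case for a change is that wording costs nothing and the loose ends are real. Section 8.2 speaks of treated patients in one sentence and evaluable patients in the next, and evaluable is not defined. Appendix 2 wants conclusions drawn from all eligible patients, which sits awkwardly with a verdict on 12 of about 16. Conditional on closure, the first-12 rate is 5 to 18 points too low. An analyst free to choose the denominator after the fact could choose the one that favours the hypothesis.

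Part of this stands. Section 8 does not state the denominator after early closure, the later batch size, or whether accrual waits for the read. The treated/evaluable wording could matter if one of the first 12 has no scan.

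The rest is weaker. A specific stopping rule stated twice governs the verdict ahead of general reporting advice in an appendix. The plan says first or initial 12 throughout, so picking an arbitrary 12 is not a reading it allows. The second-stage accrual of 23 is itself conditional on two responses, which can be read as a hold; that would shrink the overrun. Patients already on the drug at entry would also shorten the wait. Nor is the first-12 figure always the lower one: 1/12 is 8.3%, but with no later response 1/17 is 5.9%. At a true rate of 10% this happens in about 0.571 × 0.9^5 = 34% of closures.

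**Conclusion.** The overrun is plausible, but following the plan as written already gives a valid result. The cohort is negative on 0 or 1 of the initial 12, with type I error 0.098 and power 0.901. The natural reading of the estimation text is to report all evaluable normal patients, with PFS for the whole normal group. What remains is missing operational detail that analysts would fill sensibly, for instance by showing the first 12 alongside the full group.

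The gain from writing it down is about 1 point of bias averaged over closure, and between 1 and 3 points of half-width on a contrast already uncertain by about 30 points. No between-cohort test is planned, and the low-cohort data are described as hypothesis generating.

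This rests on steady accrual of 25 a year, 70% normal with no allowance for indeterminate scores, no accrual pause, and 17 normals at the read.

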### 8.3. **Analytic plan for secondary objective:**

**Definition of secondary endpoints:** Progression free survival will be measured as the times from the start of pegylated liposomal doxorubicin to the time the patient is first recorded as having disease progression or dies. If a patient does not progress or die while being followed via tumor assessment, progression-free survival will be censored at the time of last disease assessment.

We will calculate the median progression free survival in patients with low BRCA1 and normal BRCA1 protein expression. Median progression free survival will be estimated by Kaplan-Meier methodology.

## 9. **Data and Safety Monitoring Plan**

### **Data and Safety Monitoring Plan for Patients Enrolled at the University of Arizona**

The University of Arizona Cancer Center Data and Safety Monitoring Board (DSMB) reviewed the protocol and determined this study does not require DSMB oversight or routine monitoring by the QA/QC program. Principal investigator will be responsible for monitoring and reporting any changes/ adverse events to IRB. PI will be responsible all the study related activities and will report annually to IRB.

The Principal Investigator will ensure the accuracy, completeness, legibility and timeliness of the data reported in the Case Report Form (CRF). Source documentation supporting the CRF data will indicate the subject's participation in the trial and will document the dates and details of study procedures, adverse events, and patient status.

Case report forms, which include the inclusion/exclusion criteria form, adverse event forms and serious adverse event forms should be completed with a black ball-point pen or typed. Corrections to the forms should not obscure the original entry and should be made by striking the incorrect information with a single line. Each strike should be accompanied by the initials of the corrector and the correction date. All subject forms and study files will be stored in a secure area limited to authorized staff.

**Note:** Routine monitoring of regulatory documents and test article will be conducted at least annually.

### **Data and Safety Monitoring Plan for Patients Enrolled at the University of New Mexico**

The University of New Mexico Cancer Center (UNM CC) places a high priority on ensuring the safety of patients participating in clinical trials. All clinical trials require monitoring commensurate with the degree of risk involved in participation of studies. Clinical Research

Office Standard Operating Procedures (SOP's) detail functions and processes found in this plan. SOPs are available at [http://hsc.unm.edu/UNM\\_CC/intranet/ctoforms.asp](http://hsc.unm.edu/UNM_CC/intranet/ctoforms.asp).

Data and safety monitoring activities for each study continue until all patients have completed their treatment and all patients are beyond the time point at which study-related adverse events would likely be encountered. The UNM CC has implemented a process for routine, real time data monitoring and safety review of Investigator Initiated trials which takes into account the Essential Elements of the National Cancer Institute (NCI) guidelines, the FDA monitoring regulations, Good Clinical Practice Guidelines and other DSM plans and programs approved by the NCI. These are outlined in the UNM CC Data and Safety Monitoring Plan, or DSMP.

In addition to complying with NIH/NCI guidelines, the UNM CC DSMP complies with, the University of New Mexico Health Sciences Center Human Research Protections Office (HRPO) guidelines for safety and data monitoring which can be found at: <http://hsc.unm.edu/som/research/hrrc/PoliciesGuidelines.shtml>.

The DSMP is distinct from, and complements, the activities of the Protocol Monitoring & Review Committee (PRMC) and the Clinical Protocol Data Management (CPDM) functions of UNM CC. The most current version is maintained on file with the Human Research Review Committee, and is therefore not included in this protocol as an Appendix.

De-identified study results, in the form of glass slides, digitized pathology and radiology images and Microsoft Word documents and Microsoft Excel databases, will be stored for 10 years. All study results will be stored in locked offices and on password protected computers. During that time, PIs at the University of Arizona and the University of New Mexico will have access to the de-identified data for the purposes of analysis and publication.

**Process to implement study closure when significant risks or benefits are identified:** Stopping rules will be based on Simon's optimal design (Simon, R. "Optimal Two-Stage Design for Phase II Clinical Trials". Controlled Clinical Trials, 101-10, 1989, Elsevier Science Publishing Company, N.Y., N.Y.) which minimizes the expected sample size under the null response rate. In the patients with normal BRCA1 protein expression if at least two responses are observed among these 12 patients, then an additional 23 patients will be accrued to the second stage. If 0 or 1 response is observed among the initial 12 patients, then accrual to this cohort will be terminated and declared negative. At the end of the study if 6 or more patients in this cohort respond then pegylated liposomal doxorubicin will be considered worthy of further study in this cohort. This design yields at least 90% probability of a positive result if the true response rate is at least 30% and a 90% probability of a negative result if the true response rate is 10%.

### **Description of adverse events and reporting procedures:**

#### **Adverse Event**

An adverse event (AE) is any untoward medical occurrence in a patient or clinical investigation subject administered a pharmaceutical product and that does not necessarily have a casual relationship with this treatment. An AE can therefore be any unfavorable and unintended sign, symptom, or disease temporally associated with the use of a medicinal (investigational) product, whether or not related to the medicinal (investigational) product.

Adverse events of grade 3 or 4 that are possible/probably or definitely related to the study required medication or serious adverse events will be recorded on the UMC adverse events record form and reviewed by the Principal Investigator. These same events will be reported in the case report form.

All adverse events will be classified using either the MedDRA term or NCI Common Terminology Criteria for Adverse Events (CTCAE) version 4.0 and will address:

- Grade
- Relationship to study drug(not related, unlikely, possible, probable, definitely)
- Causality other than study drug (disease related, concomitant medication related, intercurrent illness, other)
- Date of onset, date of resolution
- Frequency of event (single, intermittent, continuous)
- Event outcome (resolved, ongoing, death)
- Action taken (none, held, dose reduced, discontinued, medication given)

